#### Multiplex assays: A panel of cytokines and chemokines

A panel of cytokines and chemokines (the following parameters will be analysed: IFN- $\gamma$ , IL-10, G-CSF, MCP-1, IP-10, IL-6, IL-1b) measured will be analysed in exactly the same way as IL-8.

#### Rhinovirus type-specific antibody response

The effect of probiotic on host antibody responses of the challenge virus (convalescent titer) will be analysed with one-way ANOVA, by including the change from day 0 to day 28 as a response and treatment as a fixed effect. Model assumptions will be checked with model diagnostics and normality plots. In case normality assumptions cannot be confirmed, common transformations (log, square root, inverse) will be used.

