6.4.2.2 RNA-seq: Targeted RNA-seq library preparation will be conducted with Tempo-Seq (BioSpyder) detector oligos designed against a ~1500 human gene panel focused on innate immunity and antiviral defense genes. Library preparation will be conducted in 96 sample batches. Up to 2 library preparations (n=192 samples) will be pooled, purified, quantitated and stored frozen prior to RNA-sequencing. The pooled libraries will be sent to the Pioneer core genomics facility in Johnston, Iowa for RNA-seq using an Illumina NextSeq, or HiSeq platform. The target read-depth per sample will be 1.5 million reads to ensure 500-1000 reads per gene. The reads will be quality filtered, trimmed and demultiplexed by the technical staff in Johnston. The resulting FASTQ files will be transferred via external hard drive, or through the DuPont network for further processing. Backup FASTQ files will be archived at the Johnston facility. The FASTQ files will be aligned to an annotated reference to determine the number of reads per gene. The reads will be quantitated by

normalizing with control genes in the samples set. Other quantitation methods may be considered as well. Data will be stored in this format until the samples can be decoded for further analysis. Once decoded, metadata will be added to the data files to add additional annotation to the sample identifiers and group samples according to experimental conditions. Differential expression analysis will be conducted to determine transcripts that are up or down regulated between the experimental conditions.

6.4.3 *Rhinovirus type-specific antibody response*

6.4.3.1 The effect of probiotic on host antibody responses to the challenge virus will be determined by comparing the convalescent neutralizing antibody titer in the probiotic and placebo groups.

6.4.4 *Fecal, throat and nasal microbiota*

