### 6.3 Per protocol (PP) dataset

The PP dataset will consist of all subjects having been randomized to a treatment and receiving the virus challenge on Day 0 (ITT), without any major protocol violation. Subjects with acute neutralizing titer of  $>1:4$ , respiratory virus detected prior to virus and antibiotic use before day 14 will be excluded, and only subjects with study product compliance of  $>80\%$  will be included. The subject classification to PP dataset will be done before opening of the randomisation code. PP dataset is used for all efficacy and exploratory analyses as the primary dataset, thus also for the primary evaluation of study hypothesis (see 20.2.).

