### 6.4 Infected dataset

The Infected dataset will consist of all subjects in the PP dataset, who got infected with the challenge virus. Infection will be defined as the isolation of the challenge virus on any of the 5 days (study days 1-5) after virus challenge or a four-fold rise in neutralizing antibody titer to the study virus. The Infected dataset will be used for analysis of e.g. symptom score, viral load and exploratory analyses (see 20.2).

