## 11 Analysis of efficacy

### 11.1 Primary efficacy variables

The primary efficacy analysis is comparing the incidence of rhinovirus-associated illness episodes (Yes/No) between the treatment groups. A rhinovirus-associated illness episode is detected in case both the following criteria are met:

- 1) Rhinovirus infection: Isolation of the challenge virus on any of the 5 days (study days 1-5) after virus challenge OR a four-fold rise in the neutralizing antibody titer to the study virus (day 28).
- 2) Symptomatic illness: Based on the modified Jackson criteria a total symptom score of at least 6 over the 5 days (sum of study days 1-5) after virus challenge AND either three days of rhinorrhea or the subjective impression that they have had a common cold illness.

The relationship between the treatment and the incidence of rhinovirus-associated illness episodes will be tested by using a chi-square test. In case the cell frequencies, such as the expected number of subjects experiencing an illness episode or the expected number of subjects without any episodes in either of the treatment groups, turn out 5 or lower, a Fisher's exact test will be used for the comparison instead, which is a more suitable method with low expected frequencies.

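### The exploratory antibody response is modelled as an untransformed titre change, and its fallback transformations, if applied to that change, fail for some subjects; log2 titre with the Day 0 titre as covariate avoids both problems

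*SAP*

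**What the plan says.** - **Response and model.** SAP 11.3 (Rhinovirus type-specific antibody response) uses one-way ANOVA, "by including the change from day 0 to day 28 as a response and treatment as a fixed effect". It names no scale and no baseline covariate. SAP 11.2.3 does name log10 for viral titre, and the IL-8 model in 11.3 does carry a baseline covariate.
- **Fallback.** If normality cannot be confirmed, "common transformations (log, square root, inverse) will be used". Nothing says whether the transformation acts on the titres or on the change, which of the three comes first, or what to do with zero or negative changes.
- **Dataset.** The table in SAP 20.2 marks antibody response for the Infected set only. SAP 6.4 says: "The Infected dataset will consist of all subjects in the PP dataset, who got infected with the challenge virus". The first route into it is virus isolation: "Infection will be defined as the isolation of the challenge virus on any of the 5 days". The second is "or a four-fold rise in neutralizing antibody titer to the study virus", which SAP 11.1 ties to Day 28, the same convalescent sample as this endpoint.
- **Day 0 titre.** SAP 6.3 removes subjects with an acute titre above 1:4 from PP, and so from the Infected set.
- **Protocol.** Protocol 6.4.3 plans to assess the effect by "comparing the convalescent neutralizing antibody titer in the probiotic and placebo groups". It mentions no change score and names no analysis set. SAP Section 15 does not list the move to a change score.

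**The concern.** Neutralizing titres come from serial dilutions, and the plan itself judges them by fold rises. An arithmetic difference gives equal fold rises unequal weight and lets a few high titres dominate the group means. The plan foresees a failure of normality, but two of its three remedies break down at a change of zero if they are applied to the change. A subject who shed virus without a titre rise belongs to the Infected set and has exactly that value. SAP Section 7 does not impute missing values and the SAP gives no rule for undefined ones, so such subjects could drop out.

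At stake is the precision and reproducibility of one exploratory comparison. Two analysts following the paragraph could make different permitted choices and get materially different results.

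**Working it through.** **Plan's own figure.** The documents give no sample size or power for this endpoint. The only design figure is 95 completed subjects per arm for the primary endpoint (60% v 40%). The unpooled formula reproduces it: (1.96 + 0.84)² × (0.24 + 0.24) / 0.20² ≈ 94.2, rounded up to 95. It serves here only to set the scale.

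**1. Scale.** A four-fold rise from 1:2 to 1:8 is a raw change of 8 − 2 = 6. A four-fold rise from 1:4 to 1:16 is 16 − 4 = 12. On log2 both equal 2.

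**2. Transformations applied to the change.**

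| Change | log | square root | inverse |
|---|---|---|---|
| −2 (1:4 to 1:2) | undefined | undefined | −0.5 |
| 0 (1:4 to 1:4) | undefined | 0 | undefined |
| +6 | 1.79 | 2.45 | 0.167 |
| +12 | 2.48 | 3.46 | 0.083 |

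At zero, log and inverse fail and square root works. For a fall, log and square root fail; inverse exists but breaks the ordering (−2 gives −0.5, +2 gives +0.5). If the titres are logged before differencing, every positive titre pair is usable: 1:4 to 1:4 gives 0 and 1:4 to 1:2 gives −1.

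**3. How common is zero change?** The documents do not say. Assume a log2 rise with mean 2.5 and SD 1.8, floored at 0 and rounded to whole dilutions. Then P(zero) = Φ((0.5 − 2.5)/1.8) = Φ(−1.11) ≈ 13%. With a true two-fold lower titre the mean is 1.5 and P(zero) = Φ(−0.56) ≈ 29%. Over two equal arms that is (13 + 29)/2 = 21%. So 13–21% of infected subjects would be lost to a log of the change, and unevenly between arms when there is an effect.

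**4. Power in the Infected set.** Same assumptions, 96 per arm, 90% infected in both arms, Day 0 titre 1:2 or 1:4, true two-fold difference, two-sided 0.05:

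| Analysis | Power |
|---|---|
| Raw change | about 65–67% |
| Log of change, zeros dropped | about 63% |
| Square root of change | about 90% |
| Log2 titre, with or without Day 0 covariate | about 94% |

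Residuals of the raw change failed a Shapiro test in every run, so the fallback would be triggered under these assumptions. Two permitted fallbacks then differ by 90 − 63 = 27 points.

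**5. A second set of assumptions.** Take 85 infected per arm, a mean of 3 doublings with SD 1.5, a true difference of 0.8 doublings, and 10%, 20% or 30% extra non-responders unaffected by treatment. Skewness of the raw change is above 4.

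| Extra non-responders | Raw change | Log2 fold change | Log of change, zeros dropped |
|---|---|---|---|
| 10% | 63% | 80% | 72% |
| 20% | 56% | 64% | 65% |
| 30% | 49% | 52% | 59% |

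Log2 beats the raw change throughout, by 3 to 17 points. Dropping zeros does not always cost power. Its lasting fault is that it compares only subjects whose titre rose. Type I error was about 4–6% for all three.

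**6. Selection into the Infected set.** For illustration, take shedding of 91% placebo and 76% probiotic (earlier challenge study, Protocol 1.1), and assume a four-fold rise in 50% of shedders and 30% of non-shedders in both arms.
- Infected: 0.91 + 0.09 × 0.30 = 0.937; 0.76 + 0.24 × 0.30 = 0.832.
- Admitted by titre alone: 0.027/0.937 = 2.9%; 0.072/0.832 = 8.7%.
- Four-fold rise within the Infected set: 0.482/0.937 = 51.4%; 0.452/0.832 = 54.3%.
- Four-fold rise in all PP subjects: 48.2%; 45.2%.

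The direction differs between the two sets, but each difference is only about 3 points. With 10–50% of non-shedders seroconverting, titre-only entrants are 1–5% of the placebo set and 3–14% of the probiotic set.

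**The case against.** The case for leaving the paragraph alone has real force.

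- **The plan would not keep the raw change.** It requires a normality check and a transformation on failure. If square root is chosen, the loss against log2 is about 4 points. This stands; but nothing in the SAP selects square root, and log is listed first.
- **A reader might infer that the rule cannot be executed.** The documents do not support that. Square root exists at zero change, inverse exists for a fall, and log works if titres are logged before differencing, which the wording permits. Falls also have little room, given the 1:4 cap at Day 0. Deletion of subjects is a possible consequence, not something the SAP states.
- **A reader might infer that the Infected set is selected on the response and hides a preventive effect.** Entry is only partly by titre, since isolation carries no titre condition. With infection of 91% v 76% and equal rises among the infected, the PP contrast would be about 0.15 × 2.57 = 0.39 log2 lower on probiotic and the Infected-set contrast zero. That merely restates an infection difference, which SAP 11.2.2 and 20.2 already test as a secondary endpoint in PP and ITT. How strongly infected hosts respond is a legitimate separate question.
- **A reader might infer that the protocol makes PP the main set.** Protocol 6.4.3 names no set. SAP 20.2 also allows other datasets for exploratory work. Choosing PP is a trade-off: with equal infection rates, log2 ANCOVA power was about 89% in PP against about 93% in the Infected set.

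**Conclusion.** The point holds as an improvement to one exploratory analysis. The stated default, a raw titre change with treatment only, is inefficient for multiplicative data. The first-listed fallback, if applied to the change, is undefined for subjects with no rise or a fall. Under the main assumed distribution, log2 titre gains about 27–29 points of power over the raw change, about 31 over log of the change with zeros dropped, and about 4 over its square root. Under the second set the gain over the raw change is 3–17 points.

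All these sizes rest on assumed titre distributions, because the documents give none. That the default is the raw change is inferred from the absence of a named scale. The Day 0 covariate adds almost no power here, because entry caps that titre. The Infected-set comparison is conditional on a post-randomisation outcome partly defined by the same titre; that calls for a caveat and a companion analysis, not for removal. Primary and hierarchical secondary conclusions are untouched. Severity is minor.

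**What to change.** Rewrite the antibody paragraph in SAP 11.3 to:

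1. Use log2 convalescent titre as the response, in an ANCOVA with treatment and log2 Day 0 titre.
2. Report the ratio of geometric mean titres with its 95% CI.
3. Delete transformation of the change score.
4. State the value assigned to titres below the lowest dilution. The SAP already has such a rule for undetected IL-8 (half the detection limit); the antibody endpoint has none.
5. Keep the Infected-set analysis, noting that it conditions on infection after randomisation and that a four-fold rise in the same titre is one route in. Add a PP analysis beside it, and mark both in the SAP 20.2 table.
6. Record in SAP Section 15 how the analysis departs from the protocol's comparison of convalescent titres: the change score if it is kept, otherwise the baseline adjustment and the restriction to infected subjects.

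Cost: SAP wording, one changed model and one extra run, settled before unblinding. No new data or samples are needed.

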#### Faecal, throat and nasal microbiota

For the faecal, throat and nasal microbiota at least the following analyses will be conducted. Faecal results will be analysed only descriptively.

For qPCR detecting the supplemented probiotic strain at least frequencies (Positive, Negative) by treatment and time point will be presented. If feasible, proportions can be compared with logistic regression models. For throat and nasal results the model will include the fixed effects of treatment and timepoint, the interaction of treatment and timepoint as a baseline covariate. The random subject effect will be included in the model. Also, a similar model including only observations after day 0 will be fitted to assess the effect of the virus.

For all faecal, throat and nasal microbiota, diversity of the samples will be investigated by comparing the alpha diversity (within sample diversity) values between treatments and timepoints. Alpha diversities will be calculated at DuPont and provided to 4Pharma for further analyses. For throat and nasal microbiota, the change in alpha diversity will be analysed with RM-ANCOVA in exactly the same way as described for IL-8.

From throat swabs, abundance (+, ++, +++) of 5 pathogens of special interest (*S. aureus*, pneumococcus, *H. influenza*, meningococcus and group A streptococcus) will be presented with frequency tables and analysed with cumulative logistic regression model. Probability of higher incidence will be modelled and day zero result and treatment included as fixed effects.

Correlation of abundance of the 5 pathogens with antibody response, incidence of infection or rhinovirus will be investigated with Spearman correlation coefficients.

If feasible, clustering of the samples into microbiota subtypes will be investigated separately for faecal, throat and nasal microbiota based on the weighted UniFrac metric distance matrix including all samples from all time points. UniFrac metric distance matrix will be calculated at DuPont and provided to 4Pharma for the clustering and further analyses. Unweighted pair-group method with arithmetic averages or other feasible method will be used for the clustering. The decision of the optimal number of clusters will be made based on peak values in the pseudo F and pseudo t-squared values or other suitable method. If clusters are formed, difference in proportions by treatment will be investigated with categorical analysis models and the cluster effect on secondary outcome

variables will be explored by adding the cluster effect to the analysis models as a fixed effect. Effect of cohort on clustering will be investigated with categorical repeated measures model, where clustering is the outcome variable, and timepoint, treatment, cohort, interaction of treatment and timepoint are included as fixed effects.

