4.2.2 Study periods

Screening:

- Consent and enrollment (approximately 375 subjects)
- Medical history questionnaire and demographics
- Vital signs and brief physical exam
- Physical activity question
- Review of inclusion/exclusion criteria
- Blood draw for screening neutralization antibody titer (if no antibody screening test has been done in the last 12 weeks)

Day -42 ± 4:

- All subjects begin dietary “run-in” period

Day -28 ± 4: Seronegative subjects only

- Review of inclusion/exclusion criteria
- Pre-probiotic baseline nasal lavage for IL-8 and other cytokines
- Pre-probiotic baseline nasal swab for microbiomics
- Pre-probiotic baseline throat swab for microbiomics
- Blood draw for pre-probiotic transcriptomics studies
- Assessment of concomitant medications
- Randomized to active or placebo probiotic
- Urine pregnancy screen for females

Day -21 ± 2

- All subjects return to study site for new supply of probiotic and compliance review
- AE assessment
- Assessment of concomitant medications

Day -14 ± 2:

- All subjects return to study site for new supply of probiotic and compliance review
- Nasal lavage for multiplex cytokine assays
- AE assessment
- Assessment of concomitant medications

Day -7 ± 2:

- All subjects return to study site for new supply of probiotic and compliance review
- AE assessment
- Assessment of concomitant medications

Day 0:

- Review of inclusion/exclusion criteria
- Assessment of blinding
- AE assessment
- Assessment of concomitant medications
- Urine pregnancy screen for females
- Stool specimen for probiotic compliance and microbiomics
- Nasal swab for microbiomics
- Throat swab for microbiomics
- Throat swab for culture
- Nasal lavage for unanticipated viruses
- Nasal lavage for pre-RV challenge baseline IL-8
- Blood draw for measurement of neutralizing antibody
- Blood draw for pre-RV challenge transcriptomics
- Nasal lavage for multiplex cytokine assays
- Symptom assessment
- Challenge with rhinovirus
- Compliance check/resupply
- Continue probiotic treatment

Day 1-4:

- AE assessment
- Assessment of concomitant medications
- Nasal lavage for quantitative rhinovirus culture
- Nasal lavage for IL-8 measurement
- Nasal lavage for multiplex cytokine assays
- Symptom assessment
- Assessment of the effect of symptoms on physical activity
- Nasal swab for microbiomics (day 3)
- Throat swab for microbiomics (day 3)
- Blood draw for post-RV challenge transcriptomics (Day 2 only)
- Continue probiotic treatment

Day 5:

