4.2.5 Blood for transcriptomics (Study Days -28, 0, and 2)

Blood specimens will be collected into PaxgeneRNA extractor tubes for subsequent analysis of gene expression by microarray. These specimens will be handled according to the manufacturer's instructions and stored at -70C until they are analyzed.

4.2.6 Nasal and throat swab sample collection (Study Day -28, and 0, 2, 3, 5, 14)

Nasal swabs will be collected and stored at -70C. Nasal swabs will be collected by inserting a moistened nylon flocked swab (FloQswabs, Copan Diagnostics Inc, Murrieta, CA) into each naris until resistance is met. The swab will be gently rotated and then withdrawn. Pharyngeal swabs will be done using the same swab material to swab the posterior pharyngeal wall. The nasal swabs and throat swabs will be collected before the daily dose of the study product. All throat swabs will be collected by a study nurse experienced in the procedure.

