## 20 Appendices

**20.1 Schedule of events**

	Screening	Day -28	Day -21	Day -14	Day -7	Day 0	Day 1	Day 2	Day 3	Day 4	Day 5	Day 6-14	Day 21-28
Consent	X												
Review of inclusion/ exclusion	X					X							
Serum neutralizing antibody	X*					X							X
Urine Pregnancy Screen for females		X				X							
Start of dietary run-in period	X												
Compliance check/ resupply			X	X	X	X							
Probiotic/ placebo treatment		X	X	X	X	X	X	X	X	X	X	X	
Assessment of blinding						X							
Nasal swab for microbiomics		X				X			X				
Throat swab for microbiomics		X				X			X		X	X (14)	
Throat swab for culture						X					X		
Fecal sample for microbiomics						X							
Blood for transcriptomics		X				X		X					
Nasal lavage for viral PCR						X							
Nasal lavage for IL-8/ multiplex		X		X		X	X	X	X	X	X		
Symptom assessment						X	X	X	X	X	X		
Rhinovirus challenge						X							
Nasal lavage for quantitative RV							X	X	X	X	X		

culture													
Symptom diary												X	
Assessment of Adverse Events			X	X	X	X	X	X	X	X	X	X	X
Assessment of Concomitant Medications			X	X	X	X	X	X	X	X	X		X

\*Volunteers will be screened for neutralizing antibody under an existing screening protocol at the University of Virginia (IRB-HSR #9948). Volunteers who are found to have antibody titers  $\leq 1:4$  to the study virus will be invited to consent for participation in the EPRIC study. Only volunteers who were tested more than 12 weeks prior to the screening visit will have serology repeated at this visit.

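### The post-Day-0 model of throat and nasal Bl-04 detection cannot show an effect of the virus, and for nasal swabs most of its terms are not identified

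*SAP*

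**What the plan says.** SAP 11.3, under the faecal, throat and nasal microbiota heading, promises frequencies of Bl-04 qPCR positivity by treatment and timepoint. Modelling is conditional: "If feasible, proportions can be compared with logistic regression models".

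For throat and nasal swabs the model has fixed effects of treatment and timepoint, followed by "the interaction of treatment and timepoint as a baseline covariate". The SAP then adds "The random subject effect will be included in the model". No baseline day is named. The second model follows: "Also, a similar model including only observations after day 0 will be fitted to assess the effect of the virus". Neither model has a term for infection.

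The schedules in the protocol and in SAP 20.1 put nasal swabs on Days -28, 0 and 3, and throat swabs on Days -28, 0, 3, 5 and 14. The visit list in Protocol 4.2.2 agrees for the post-challenge nasal sample: "Nasal swab for microbiomics (day 3)".

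Both arms are challenged on Day 0 (Protocol 5.3.1), and challenge is a condition of entry to the ITT and per-protocol sets (SAP 6.2, 6.3). SAP 20.2 makes the per-protocol set the main dataset for these swabs, with the Infected dataset as secondary.

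**The concern.** The second model is given a purpose that its data and terms cannot serve. An effect of the virus needs either samples from before and after challenge, or subjects who differ in exposure or infection. Restricting responses to days after Day 0 removes the first. Challenging everyone and naming no infection term removes the second.

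The practical risk is mislabelling. Software will often drop aliased terms and still print a result. What remains is a between-arm difference after challenge, and under the SAP's label it could be reported as an effect of the virus on Bl-04 detection. For nasal swabs there is a further risk: if the subject effect is kept, the size of the treatment coefficient depends on a variance that the data do not determine.

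**Working it through.** The plan states no figure on this point, so there is none to reproduce. The check is a count of sampling days followed by the rank of the design.

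**1. Sampling days** (protocol schedule, Protocol 4.2.2, SAP 20.1)

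| Swab | Day 0 or earlier | After Day 0 |
|---|---|---|
| Nasal | -28, 0 | 3 |
| Throat | -28, 0 | 3, 5, 14 |

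**2. Can a virus effect be separated from the intercept?** Let V = 1 if day > 0 and 0 otherwise. In the restricted data V = 1 in every row, so it duplicates the intercept.

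- Nasal: intercept, treatment, V = 3 columns, rank 2.
- Throat: intercept, treatment, 2 timepoint columns, 2 interaction columns, V = 7 columns, rank 6.
- With a baseline covariate added: nasal rank 3 of 4, throat rank 7 of 8. The deficit remains.

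**3. Nasal fixed effects as listed.** On Day 3 alone, with t = 0 or 1 for arm, the columns for intercept, treatment, timepoint and treatment-by-timepoint are (1, t, 1, t): 4 columns, rank 2. Only the level in one arm and the Day 3 treatment difference can be estimated.

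**4. Nasal random subject effect.** Each subject contributes one yes/no result. The data supply two proportions, while intercept, treatment and subject SD make three parameters. For a given SD σ, the coefficient b for an arm solves

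p = ∫ expit(b + σu) φ(u) du.

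The documents give no expected detection rates, so 20% and 40% on Day 3 are assumed for illustration:

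| Subject SD σ | Treatment log-odds ratio |
|---|---|
| 0 | 0.98 |
| 1 | 1.16 |
| 2 | 1.56 |
| 3 | 2.05 |

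All four rows reproduce the two proportions exactly, so they fit equally well. The odds ratio runs from exp(0.98) ≈ 2.7 to exp(2.05) ≈ 7.8. An ordinary logistic model is the σ = 0 row. Using Day 0 status as a covariate still leaves one response per subject. Any estimate of σ would then rest on the assumed shape of the link, not on repeated measurement.

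**5. If the Day 0 swab is kept as a response level.**

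- Nasal, Days 0 and 3: 2 arms × 2 days = 4 columns, rank 4. With a Day -28 covariate, rank 5 of 5.
- Throat, Days 0, 3, 5 and 14: 2 × 4 = 8 columns, rank 8. With a Day -28 covariate, rank 9 of 9.

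The change from Day 0, and its difference between arms, can then be estimated.

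**The case against.** Several things can fairly be said for the plan.

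**The label may simply be loose.** The baseline phrase looks like a slip, perhaps for a list ending with the interaction and a baseline covariate. The IL-8 model in SAP 11.3 uses the Day -28 or Day 0 value as covariate, and the throat-pathogen model includes the Day 0 result. A similar model here may be meant to carry Day 0 status as covariate. This is plausible, and the phrase should not be read as an error of method. But that model estimates a treatment difference after challenge adjusted for Day 0, which is still not an effect of the virus.

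**The first model already holds the contrast.** It is not restricted by day, so Day 3 against Day 0 and its interaction with treatment can be obtained there. This stands, and it means that no additional model is needed.

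**Pre-challenge samples are not the only route.** A reader might infer that the restricted data contain no virus-free subject. The documents do not support that. Protocol 4.2.10 gives an infection rate of 85-90% in susceptible volunteers and Protocol 8.1 about 90% in controls, so some 10-15% of those challenged would be expected to stay uninfected. Culture is scheduled only for Days 1-5, so nothing shows that Day 14 throat samples carry virus. Infected versus uninfected is therefore a possible comparison, and SAP 11.3 plans such a factor for transcriptomics clustering. It is not named in this model.

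**The nasal model might still run.** A reader might infer that it cannot be fitted at all. That is too strong: the Day 3 treatment difference is estimable, and the plan says similar, not identical.

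**There may be a second nasal day.** The heading of Protocol 4.2.6 reads "Nasal and throat swab sample collection (Study Day -28, and 0, 2, 3, 5, 14)". It covers both swab types, no schedule row or visit list shows a Day 2 swab, and another post-challenge day would add no pre-challenge comparison.

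**The wider objective is safe.** A reader might infer that the objective in Protocol 2.2.3, to describe the microbiomes before and during infection, is lost. It is not. That objective concerns composition, which the alpha-diversity and clustering analyses address; this model concerns detection of one strain.

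**Conclusion.** The point holds. As written, the restricted model cannot deliver its stated aim: it contains no before/after contrast and no infection contrast. For throat swabs it yields treatment differences and trends over Days 3, 5 and 14. For nasal swabs it yields only the Day 3 treatment difference, and the timepoint, interaction and subject terms are not identified.

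The size is small. The analysis is exploratory and fitted only if feasible, the frequencies are reported regardless, and SAP 11.3 says that part of the microbiota work will stay out of the Statistical Study Report. No primary, secondary or safety conclusion is touched.

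The conclusion assumes that observations after Day 0 exclude Day 0 itself, that the schedule rows rather than the 4.2.6 heading give the swab days, and that Day 0 swabs precede inoculation, as their order in the Protocol 4.2.2 visit list suggests. The 20% and 40% rates only illustrate the problem; the identification result does not depend on them.

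**What to change.** 1. Take the virus-related contrast from a model that keeps the Day 0 swab as a response level: Day 3 against Day 0 for nasal swabs, and Days 3, 5 and 14 against Day 0 for throat swabs, with treatment-by-timepoint to show whether the change differs by arm. The main model with Day -28 status as baseline covariate already does this, so a duplicate is unnecessary.
2. Report the result as a before/after change. Since every subject is challenged, it is confounded with time and with continued supplementation.
3. Optionally add infection (yes/no), as in the transcriptomics section. This must be done in the per-protocol set, because infection is constant in the Infected dataset. Infection is also a post-randomisation outcome, so the comparison is not a randomised one.
4. If the post-Day-0 model is kept, call it the treatment difference after challenge adjusted for Day 0 status. For nasal swabs use ordinary logistic regression on Day 3, without timepoint, interaction or subject effect.
5. Rewrite the baseline phrase so that treatment-by-timepoint is a fixed effect and the baseline day is named.

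The cost is SAP wording only. The Day -28 and Day 0 swabs are already in the schedule, and no sample or visit is added.
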